1.2 Schema

1.3 Schedule of Activities (SOA)

Procedures	Screening Appt.	Initial Appt. +/- 30 days	MRI Appt. +/- 30 days	Anesthesia Clearance	Randomization	Pre-op	Day of Surgery	2 wk Post-op +/- 5 days	2 m Post-op +/- 10 days	12 m Post-op +/- 10 days	24 m Post-op +/- 30 days
Demographics		X									
Medical history		X									
Surgical history		X									
Randomization				X							
Pre-op with surgeon					X						
Inclusion/exclusion criteria	X										
Research consent		X									
Surgical consent						X					
Surgical procedure							X				
Surgeon's Report							X				
Physical exam	X							X	X	X	X
Dynamic pelvic ultrasound	X								X	X	X
MR defecography			X								
Anesthesia Clearance				X							
Bowel habit	X							X	X	X	X
POPQ assessment	X								X	X	X
PFDI assessment	X								X	X	X
Pain scale	X							X	X	X	X
Pain medication use	X							X	X	X	X
Activity scale	X							X	X	X	X
Impression of improvement									X	X	X
PFIQ									X	X	X
SF-36								X	X	X	X
EQ-5D									X	X	X
Brink scale									X	X	X
Research Participation											X
Adverse event/unanticipated problems			X	X	X	X	X	X	X	X	X

2. Introduction

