Participants will receive the allocated transvaginal sacrospinous rectopexy surgery along with or without CVPS or laparoscopic abdominal ventral rectopexy surgery with or without CVPS as indicated for each individual and as determined before surgery (exceptions are allowed during the surgery if the surgeon decides that changing the surgical plan is in the best interest of the patient; this will be recorded as a protocol deviation). CVPS includes vaginal prolapse repair surgeries (anterior vaginal repair, posterior repair, and vault suspension) and abdominal prolapse repair surgery (sacrocolpopexy). If the participants report stress urinary incontinence at baseline, they will also receive a Tension-Free Vaginal Tape (Advantage FitTM, Boston Scientific). The primary objective of the surgical intervention is to compare the surgical success of rectal hypermobility surgery using TSR to surgery using LAVR 24 months postoperatively. The secondary objectives include comparing the change in pelvic floor disorder symptoms including OD and fecal incontinence symptoms, QOL and the incidence of perioperative and postoperative complications of these two rectal suspension procedures. We will also describe the motivations and barriers for individual women's participation in women's health research at 24 months after surgery in all participants. Data collection will occur at baseline, surgery and during hospitalization, and at 2 weeks, and 2-, 12-, and 24-months postoperatively.

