3. QOL

- a. Global: compare SF-36 scores and sub-scales (73), EQ-5D. (71, 74)
- b. Disease-specific: compare urinary, bowel and prolapse scales of PFIQ score (65)

4. Participants' Perception of Motivation and Barriers to Continued Study Participation questionnaire

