9.2 Sample Size Determination

Based on our preliminary studies in literature (83-87), we assume an anatomic success rate in LAVR group is about 70% at 24 months. The investigators believe that a difference in success rates less than 25% will not change clinical practice, but also that the sample size should be large enough so that an observed difference in success rates of 20% would be significant; i.e., an inability to differentiate between the procedures will require an observed difference that is less than 20%.

The study will be individually randomized group-treatment trial (IRGT), which patients are randomized to surgical interventions through a common surgeon (88-90). There will be three surgeons performing each surgical treatment. The number of surgeons and patients will be the same in each clinical site. We anticipate an average of 16 individually randomized patients per surgeon in each treatment group. Outcomes for patients treated by the same surgeon tend to be more similar. We assume minimal variability, estimating a small intraclass correlation coefficient (ICC) of 0.01. The table below illustrates power to detect at least 23% difference between treatment groups with varying assumptions on ICC and dropout rates. A total of 96 patients (48 patients per group) would yield 86% power to differentiate between anatomical success rates of 70% and 93% assuming an ICC of 0.01 and a two-sided 5% level of significance. Projecting a 20% dropout/loss to follow up rate over 2 years, we anticipate recruiting and up to 120 total patients.

ICC	% Dropout	Total patients	Average patients per surgeon	Power
0.01	0	120	20	92%
	10	108	18	90%
	20	96	16	86%
0.02	0	120	20	90%
	10	108	18	87%
	20	96	16	83%
0.05	0	120	20	82%
	10	108	18	79%
	20	96	16	76%

Due to concerns that ICC is higher than expected or dropout rate is higher than 20% toward the end of 2-year follow-up, we calculated the sample size that would be needed for 87% power to differentiate between anatomical success rates of 70% and 95% (a difference of 25%) in treatment groups with a two-sided 5% level of significance. The required sample size is 39 per group, or 78 total patients.

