APPENDIX E – Schedule of Forms

	Screening Appt	Initial Appt +/- 30 days	MRI Appt +/- 30 days	Anesthesia Clearance	Randomization	Pre-op	Day of Surgery	2 wk PO +/- 5 days	2 m PO +/- 10 days	12 m PO +/- 10 days	24 m PO +/- 30 days
Form 01 Eligibility		X									
Form 02 Demographics		X									
Form 03 Medical History		X									
Form 04 Baseline PE	X										
Form 05 Follow-up PE									X	X	X
Form 06 Surgeon's report							X				
Form 07 2 week post-op visit								X			
Form 08 Activity Assessment	X							X	X	X	X
Form 09 Pain Scale	X							X	X	X	X
Form 10 EQ-5D									X	X	X
Form 11 SF-36								X	X	X	X
Form 12 PFIQ									X	X	X
Form 13 PFDI	X								X	X	X
Form 14 Global Impression									X	X	X
Form 15 Bowel Habit	X							X	X	X	X
Form 16 Research Participation											X
Form 17 Adverse Event		X (if applicable)	X (if applicable)	X (if applicable)	X (if applicable)	X (if applicable)	X (if applicable)	X (if applicable)	X (if applicable)	X (if applicable)	X (if applicable)
Form 18 Unanticipated Problem		X (if applicable)	X (if applicable)	X (if applicable)	X (if applicable)	X (if applicable)	X (if applicable)	X (if applicable)	X (if applicable)	X (if applicable)	X (if applicable)
Form 19 Protocol Deviation		X (if applicable)	X (if applicable)	X (if applicable)	X (if applicable)	X (if applicable)	X (if applicable)	X (if applicable)	X (if applicable)	X (if applicable)	X (if applicable)
Form 20 Study Exit		X (if applicable)	X (if applicable)	X (if applicable)	X (if applicable)	X (if applicable)	X (if applicable)	X (if applicable)	X (if applicable)	X (if applicable)	X (if applicable)

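### The questionnaire on barriers to continued participation is scheduled only at 24 months, so it would describe the women who stayed, not all participants

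*Combined protocol and SAP*

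**What the plan says.** Section 4.1 (Overall Design) closes its list of objectives with a descriptive one: motivations for, and barriers to, women's taking part in "research at 24 months after surgery in all participants". The efficacy list in Section 8.1 names the instrument as its item 4: "Participants' Perception of Motivation and Barriers to Continued Study Participation questionnaire".

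Two tables fix the timing, and they agree. In the Schedule of Activities (Section 1.3) the row "Research Participation" has one mark, in the 24-month column. In Appendix E the row "Form 16 Research Participation" also has one mark, in the same column. No section provides for giving the form at withdrawal, by telephone or by mail.

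On attrition, Section 9.2 states: "Projecting a 20% dropout/loss to follow up rate over 2 years, we anticipate recruiting and up to 120 total patients".

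For women who leave early, the plan has three provisions:
- Section 7.2 has the reason for discontinuation or withdrawal entered on the case report form.
- Section 7.3 requires attempts to contact a woman who misses a visit. If she stays unreachable, she is classed as withdrawn with loss to follow-up as the reason.
- Appendix E lists Form 20 (Study Exit), to be used if applicable from the initial appointment onward. Its content is not shown.

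**The concern.** The instrument asks about staying in the study, and a woman has to stay until the last visit to receive it. Selection into the answering sample is therefore tied to the thing being measured. That is a closer link than in ordinary attrition, where leaving may have little to do with the measure.

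At stake is a descriptive finding about why women take part in and remain in this kind of research. If it is reported for all participants, it would rest on those who attended at 24 months. Women who left because of a barrier would be absent from the figures, and their answers cannot be collected afterwards.

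**Working it through.** **Inputs**
- Evaluable patients: 96 (Section 9.2).
- Projected dropout or loss over two years: 20% (Section 9.2).
- Administration of Form 16: 24-month visit only (Section 1.3 and Appendix E).
- Share of women reporting a given barrier: not given in the documents, so any value below is an assumption.

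**Step 1. Reproduce the plan's total.** Recruited = evaluable / (1 − dropout) = 96 / 0.80 = 120. This matches Section 9.2.

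**Step 2. Expected number not asked.** 120 × dropout rate:

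| Dropout | Asked | Not asked |
|---|---|---|
| 10% | 108 | 12 |
| 20% (plan's projection) | 96 | 24 |
| 30% (assumed) | 84 | 36 |

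These are expected numbers based on a planning allowance, not counts.

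**Step 3. What the completers' figure can say about everyone.** Let x be the share of completers who report a barrier and y the unobserved share among leavers. At 20% dropout:

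overall share = 0.8x + 0.2y

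With nothing assumed about leavers, y runs from 0 to 1, so the overall share lies between 0.8x and 0.8x + 0.2:
- x = 10%: from 0.8 × 0.10 = 8% to 0.08 + 0.20 = 28%.
- x = 20%: from 0.8 × 0.20 = 16% to 0.16 + 0.20 = 36%.

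The band is 20 percentage points wide whatever x is.

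**Step 4. Bias under assumed shares.** Bias of the completers' figure = x − (0.8x + 0.2y) = 0.2(x − y):
- x = 10%, y = 40%: overall 0.08 + 0.08 = 16%, so 10% is 6 points too low.
- x = 20%, y = 50%: overall 0.16 + 0.10 = 26%, so 20% is 6 points too low.
- x = 30%, y = 30%: overall 30%, no bias.
- x = 10%, y = 0%: overall 8%, so 10% is 2 points too high.

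The sign and the size both depend on y, which the current schedule leaves unobserved.

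**The case against.** The strongest reply is that Section 4.1 fixes the time point at 24 months itself and the two schedules follow it. The preceding objectives compare the two procedures, so the reference to all participants may mean both arms pooled rather than every woman including those who left. On that reading the sections agree, and what remains is attrition in a 24-month measure. The reading is possible, so a reader should not infer an outright contradiction between Section 4.1 and the schedules. Even so, the result would still describe only women attending at 24 months, and nothing in the plan says so.

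A reader might also infer that the trial learns nothing about why women leave. The documents do not support that. Section 7.2 records a reason, Section 7.3 requires contact and asks whether the woman wishes to continue, and Form 20 may hold more. What stands is narrower. None of these is the named questionnaire, none is said to cover motivations, and a coding of lost to follow-up states no barrier.

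A third tempting inference is that everyone who answers has already overcome the barriers, so that barriers are understated by design. The items of Form 16 are not shown, completers can report barriers they met, and some women leave by investigator decision (Section 7.2). Understatement is the natural expectation but is not documented.

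Finally, the objective carries little weight. It is not among the outcomes in Section 3, and Section 9 plans no analysis of it. That is correct, and it limits the importance of the point.

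**Conclusion.** The point holds as a minor one. Followed as written, the plan gives an instrument on continued participation only to women who continued. At the plan's own 20% projection, about 24 of 120 women would be expected not to receive it, and any barrier share for all participants is then known only to within 20 percentage points. This rests on the projected dropout being realised and on no off-schedule use of Form 16. The expectation that barriers are understated is plausible, but its direction and size depend on assumed shares among leavers.

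No treatment comparison, safety result or primary analysis is affected. Label: cheap improvement.

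**What to change.** 1. In Appendix E and the Schedule of Activities, give Form 16 together with Form 20 (Study Exit) whenever a woman leaves before 24 months and can be reached.
2. Report the results separately for 24-month attenders and early leavers, with the number of women not asked.
3. In Section 4.1, state that the 24-month figure applies to women attending that visit.

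Form 20 is already scheduled, so no visit is added. At 20% dropout the change could reach up to 24 further women, less those who cannot be contacted. Giving the form to everyone at an earlier visit as well would reach more of them, but it measures a different time point. If that is done, its results should be kept apart from the 24-month results.

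The cost is a small burden on women who are leaving, a schedule and REDCap edit, and IRB approval of the amendment, which the compliance statement at the front of the protocol requires. Women who cannot be reached would still be missed, which is why the number not asked should be reported.

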4.2 Scientific Rationale for Study Design

Ultrasound indicators of rectal support defects in women with obstructive defecatory symptoms (48)

This retrospective cohort study included 65 women who were referred to our urogynecology clinic because of varied pelvic floor disorders between January 2013 and January 2014. Patients completed a standardized interview including PFDI-20 questionnaire and received a standard examination, and assessment of their pelvic floor by 3D EVUS. Women were categorized to case (with OD symptoms) and control (without OD symptoms) based on their answers to Questions 7, 8 and 14 on the PFDI-20 (CRADI) questionnaire. In ultrasound images, women with OD symptoms had a significantly shorter span of attachment between the rectum and posterior vaginal

[figure not shown]

Figure 1: 2D dynamic endovaginal posterior compartment ultrasound of a patient with obstructed defecation symptoms at rest (left image) and at strain (right image). Rendering of an aluminum can is used to illustrate the concept of the rectal compression seen above. LP: Levator Plate, RVS: Rectovaginal Septum

wall (i.e. deeper cul de sac), and also had significantly increased descent of the cul de sac toward the anorectal junction when intraabdominal pressure was increased (Figure 1). A hypermobile ‘sliding rectum’ was observed that appeared to alter the fundamental biomechanics of defecation. These rectal mobility findings were extremely consistent among women reporting OD symptoms and not seen among asymptomatic controls.

Compression Ratio Measured Via Dynamic Ultrasound and Validated Against MR Defecography is a Strong, Independent Predictor of OD

As part of the above study, we established and validated a novel dynamics ultrasound measure (“compression ratio”) to quantify this observed rectal sliding / hypermobility. The term “compression” was initially utilized because the rectum, during dynamic ultrasound, appeared to behave like an empty aluminum beverage can being compressed from its ends (Figure 1, bottom). As the cul de sac descended toward the anorectal junction with increased intraabdominal pressure, the rigid support of the probe anteriorly (i.e. bottom of ultrasound image) caused the descent of the cul de sac to be linear, making it appear as if it was sliding and folding on itself relative to the posterior vaginal wall. In participants without OD symptoms, little to no sliding was observed. The compression ratio (see approach for details) in our study proved to represent a strong and independent predictor of both the presence or absence of OD symptoms and the severity. The risk of OD symptoms was 32 times greater among those with a high compression ratio (≥ 14) compared to those with low compression ratio (< 14), after controlling for age, BMI, parity, stool type, and BM frequency per week. A similar compression ratio was also calculated using measurements obtained by MR defecography. While MR measurements added meaningfully to our conclusions, the absence of a probe anteriorly resulted in a less vivid “crushed can” appearance when compared to dynamic ultrasonography. Thus, the less expensive and more patient-friendly in-office dynamic ultrasound appeared to be superior to MRI with regard to OD evaluation.

OD Symptoms lack a correlation to rectocele

It is worth emphasizing that along with the strong and robust correlations observed between OD symptoms and US-detected rectal hypermobility, our findings indicated a clear lack of correlation between OD symptoms and the presence or absence of rectocele as diagnosed via pelvic examination. While posterior vaginal compartment prolapses (i.e. rectoceles) may certainly account for bothersome symptoms including vaginal bulging and laxity, rectoceles appear to have essentially no relationship to obstructive defecation which was related to only one anatomic finding: excessive mobility of the rectum that is usually occult and easily detected by ultrasound. This core observation would, arguably, make it unsurprising that rectocele repairs have performed poorly to resolve obstructive defecation symptoms (24, 25). Furthermore, this diagnostic/anatomic finding provided the basis for our proposed surgical approach, transvaginal sacrospinous rectopexy.

OD symptoms persist after conventional vaginal prolapse repairs at 2 years follow up (5)

The previous finding regarding the role of POP was further demonstrated when we performed a sub-analysis of two major clinical trials performed by the Pelvic Floor Disorders Network: the Colpopexy and Urinary Reduction Efforts (CARE) trial and the Operations and Pelvic Muscle Training in the Management of Apical Support Loss (OPTIMAL) trial (55, 56). The study aimed to address 2 questions: 1) is any conventional vaginal prolapse repair effective in curing OD symptoms, and 2) is there evidence to suggest that a sacrocolpopexy will increase the risk of worsening or newly onset OD symptoms?

Regardless of trial, OD symptoms were present in more than half of the patients at the initial visit before the surgical intervention and interestingly about one third of the patients were symptomatic at the 24-month follow-up interval in all conventional vaginal prolapse surgeries, with or without posterior vaginal wall repair (353 participants from OPTIMAL and 279 participants from CARE). It is also important to note that about 1/4 of the patients experienced worsening of their OD symptoms in the absence of anatomical failure. These data further support our overall hypothesis for this proposal that OD symptoms primarily result from structural defects in rectal support and not as a result of a loss in vaginal support, challenging the current standard for surgical treatment.

Statistical shape modeling during evacuation suggests pelvic floor defects contribute to OD (57)

This study used MR defecography and statistical shape modeling to identify variation in pelvic floor shape. 16 women underwent MR defecography and were sorted by Group: case with OD symptoms (N=9) vs control (N=7) (57). The pelvic floors were segmented at the mid-sagittal slice as spline curves and a statistical shape analysis was performed. These results support the hypothesis that the mid-sagittal shape of the pelvic floor deforms significantly during evacuation and differs significantly between women with and without OD symptoms. Women with OD symptoms had a hyper-relaxed pelvic floor—with lower, straighter levator plates and straighter level III support (Figure 2). Interestingly, levator plate relaxation and perineal body straightening were similar during evacuation, indicating that the differences between groups observed in this study were structural rather than functional defects.

[figure not shown]

Figure 2: Illustrations of midsagittal pelvic floor traces (the midsagittal slice of the pelvic floor muscles, including the levator ani and level III vaginal support structures, that run from the pubic symphysis to the tip of the coccyx) from 3 asymptomatic control women (blue) and 3 women with obstructed defecation symptoms (red) at rest and during peak evacuation. These midsagittal traces were segmented from MR defecography images. On average, the control levator plates appeared better supported (as demonstrated by more dramatic curvature and elevation) than levator plates at both rest and peak evacuation in ODS participants¹⁷. This supports that levator plate relaxation (as demonstrated by a straighter and more vertical levator plate) is likely either a contributing mechanism or the result of obstructed defecation symptoms.

Transvaginal sacrospinous rectopexy is safe and feasible for treating OD (15)

This was a prospective case series study performed during December 2018-July 2020 and aimed to investigate the safety, efficiency, and durability of transvaginal sacrospinous rectopexy in women with OD symptoms and significant rectal hypermobility/folding (15). 20 patients underwent the procedure and completed the follow up at 2 and 12 months postoperatively. Statistically significant improvements were observed in all OD symptoms and subjective improvement ($94.7\% \pm 13.4$ and $90.6\% \pm 18$) at 2 and 12 months after the surgery, respectively. Mean rectal compression ratio, detected via ultrasound, improved from $45.5\% \pm 18.4$ preoperatively to $9.2\% \pm 13.7$ at 2 months ($p <0.0001$) and $19.6\% \pm 14.4$ at 12 months ($p<0.0012$). Surgical failure, defined as combined subjective (OD symptoms $> 50\%$ of bowel movements) and anatomical failure (rectal compression ratio $>25\%$), occurred in two patients. Overall, this study demonstrated that transvaginal sacrospinous rectopexy was safe, feasible, and effectively treated OD symptoms within this cohort of women undergoing POP surgery with rectal hypermobility confirmed by dynamic ultrasound.

The proposed Latin hypercube parametric study based on finite element analysis and statistical shape modeling was successful in identifying the relative contributions of urethral support (53, 54)

In a recent set of publications (53, 54), we utilized the finite element method and statistical shape modeling to elucidate the role of supportive tissues on the urethra during Valsalva. While these papers focused on the urethra, the methods and workflow will be similar to that utilized by this proposal. A finite element model of the urethra and its supports was created (Figure 3).

Material properties were varied using Latin hypercube sampling to perform a sensitivity analysis resulting in 50 simulation outcomes where the motion and shape of the urethra was predicted and compared to those obtained from clinical measurements from 76 total patients ranging from no, mild, to severe SUI (excluding women with a low urethral closure pressure, i.e. focusing on patients whose level of continence was likely resulting from the integrity of their structural support). The results showed that a reduction of the urethral stiffness and/or the parameters governing the stiffness of the perineal membrane resulted in simulated urethral motions and shapes associated with stress urinary incontinence. This represents a novel use of finite element modeling and statistical shape modeling to provide a mechanical basis explaining underlying clinical observations.

[figure not shown]

Figure 3: Screenshots of the baseline finite element model at rest (top) and peak Valsalva (bottom). A) Images from the perspective of the sacrum facing anteriorly and inferiorly. B) Images from the patient's right side with a midsagittal cut so the urethra can be seen clearly. C) Displays the same model view as B, but with the patient's dynamic MRI images overlaid to demonstrate the agreement between the final model and in vivo imaging.

